2.0 LIST OF ABBREVIATIONS

ADaM	Analysis Data Model
bpm	beats per minute
CV%	percent coefficient of variation
AE	adverse event
AUC _∞	area under the plasma concentration-time curve from time 0 to infinity
AUC _{last}	area under the plasma concentration-time curve from time 0 to time of the last quantifiable concentration
BMI	body mass index
C _{max}	maximum observed plasma concentration
CS	clinically significant
C-SSRS	Columbia - Suicide Severity Rating Scale
DIC	drug-in-capsule
ECG	Electrocardiogram
eCRF	electronic case report form
ET	early termination
GMLT	Groton Maze Learning Test
KSS	Karolinska Sleepiness Scale
MedDRA	Medical Dictionary for Regulatory Activities
N	number of subjects
NCS	not clinically significant
PD	pharmacodynamic
PK	Pharmacokinetic
PO	single oral
PT	preferred term
qEEG	quantitative electroencephalography
SAE	serious adverse event
SC	Subcutaneous
SD	standard deviation
SOC	system organ class
t _{1/2z}	terminal disposition phase half-life
TEAE	treatment-emergent adverse event
t _{max}	time to first occurrence of C _{max}

3.0 OBJECTIVES

Note: Enrollment was paused in July 2017^{CCI} [REDACTED]. At that time, Part 1 was complete and 12 subjects had enrolled in Part 2. The Part 2 subjects were discontinued at that time. Subsequently, in January 2018, the global product team decided not to resume enrollment in the study. Therefore, only certain safety and pharmacokinetic (PK)-related endpoints will be analyzed. The original study objectives are given below.

1.2. PRIMARY OBJECTIVE

The primary objective of this study is as follows:

- To assess the effect of a single oral (PO) dose of TAK-071 on the attenuation of cognitive deficit induced by scopolamine (0.5 mg subcutaneous [SC]) as measured by Groton Maze Learning Test (GMLT) (total number of errors).

1.3. SECONDARY OBJECTIVES

The secondary objectives of this study are as follows:

- To characterize the safety and tolerability of a single PO dose of TAK-071 when co-administered with SC scopolamine (0.5 mg) in healthy subjects.
- To characterize the single PO dose plasma PK profile of TAK-071 when co-administered both with scopolamine and a low-calorie, low-fat breakfast in healthy subjects.
- To demonstrate assay sensitivity by using donepezil 10 mg as the positive control.
- To assess the effect of a single PO dose of TAK-071 in combination with 10 mg donepezil on the attenuation of cognitive deficit induced by scopolamine (0.5 mg [SC]) as measured by GMLT (total number of errors).

1.4. EXPLORATORY/ADDITIONAL OBJECTIVES

The exploratory objectives of this study are as follows:

CCI

1.5. STUDY DESIGN

4.4.1. OVERVIEW

This study consists of 2 parts.

Part 1 is an open-label initial substudy to explore the PK profile of TAK-071 in the presence of a light meal and co-administration of scopolamine to determine TAK-071 dose for Part 2, the main study.

Part 2 is the main study to assess the effects of TAK-071 on scopolamine-induced cognitive impairment.

4.4.2. STUDY DESIGN – PART 1

This is a nonrandomized, open-label, 1-treatment, 1-period, 1-sequence phase 1 study to characterize the plasma PK of TAK-071 when administered under the same conditions as in Part 2, the main study. This is in conjunction with scopolamine, and together with a low-calorie, low-fat breakfast in healthy adult male subjects. Approximately 6 healthy subjects are enrolled in this substudy with a minimum of 4 completers.

A schematic of Part 1, the substudy, design is provided in [Figure 4.a](#).

Figure 4.a Schematic of Study Design – Part 1

Pretreatment Period		Treatment Period		Final Visit	PK Follow-Up	Follow-up
Screening	Check-in	Single Dose/PK	PK	Check-out/PK	PK	Follow-up Telephone Call
Days -28 to -2	Day -1	Day 1	Days 2-4	Day 5	Day 8	Day 12 (± 2)
	← Confinement →					

Subjects check-in at the study site on Day -1 and are confined until the completion of assessments on Day 4. A follow-up PK assessment is performed on Day 8 and a final follow-up occurs on Day 12 (± 2).

Scopolamine is administered as a single 0.5 mg SC injection.

[figure not shown]
TAK-071 is administered as a single PO dose (as drug-in-capsule [DIC]) 24 hours before scopolamine administration.

Blood samples for the analysis of TAK-071 plasma concentrations are obtained at specified time-points up to 168 hours after TAK-071 dosing (144 hours after scopolamine dosing).

Safety and tolerability of TAK-071 in combination with scopolamine are assessed from physical examination, adverse events (AEs), clinical laboratory tests, electrocardiograms (ECGs), etc.

The planned timing of assessments and meals relative to scopolamine dosing in Part 1 is shown in [Figure 4.b](#).

Figure 4.b TAK-071 PK Assessments and Meal Timing Relative to Scopolamine Administration – Part 1 (Days 1 and 2)

4.4.3. STUDY DESIGN – PART 2

This is a randomized, double-blind, sponsor unblinded, placebo-controlled, 5-treatment, 5-period, 10-sequence crossover phase 1b proof of mechanism study to evaluate the effects of a single PO administration of TAK-071, a novel M₁R PAM, on scopolamine-induced deficits in cognitive function in healthy adult male subjects.

Approximately 40 subjects are expected to be randomized in this study, with the total of 4 subjects per sequence, with a minimum of 3 completers. A schematic of the study design is provided in [Figure 4.c](#).

Figure 4.c Schematic of Study Design – Part 2

Screening Period	Treatment Periods 1 to 5				Wash-Out Periods 1 to 4	Follow-Up
Screening and Pre-Enrollment Enrichment	Check-in	Baseline PD	Single Dose PK/PD	PK/PD		Follow-up Telephone Call/Visit
Days -56 to -2	Day -1	Day 1	Day 2	Day 3	Days 4 to 20	Day 9 (±2) Period 5
	← Confinement →					

4.4.3.1. PRE-ENROLLMENT ENRICHMENT SCREENING – PART 2

To ensure that enrolled subjects show cognitive impairment in the presence of scopolamine but with minimal sedation and/or fatigue, all subjects who meet Screening inclusion/exclusion criteria are administered an SC dose of scopolamine 0.5 mg.

Pre-enrollment enrichment procedures are conducted as part of the Screening assessments between 56 and 2 days before Day 1, and the results are used to accept/reject the subject for enrollment to Part 2, the main study.

Subjects remain under observation post-scopolamine administration per principal investigator's discretion to ensure that scopolamine-induced effects have worn off and it is safe for the subjects to leave the study center.

Any subjects unable to perform the CogState battery after training are excluded from entering Part 2, the main study.

4.4.3.2. TREATMENT SEQUENCES – PART 2

In each period, subjects check-in at the study site on Day -1 and are confined until Day 3 (approximately 24 hours postdose of scopolamine or matching placebo).

Subjects are randomly assigned to 1 of 10 possible treatment sequences before the first dose of study drug, each consisting of 5 treatment periods (Table 4.a).

Table 4.a Summary of Treatment Sequences in Study - Part 2

Sequence	Period 1		Period 2		Period 3		Period 4		Period 5
1	A	Minimum 3-week washout	B	Minimum 3-week washout	D	Minimum 3-week washout	E	Minimum 3-week washout	C
2	B		C		E		A		D
3	C		D		A		B		E
4	D		E		B		C		A
5	E		A		C		D		B
6	A		C		B		E		D
7	B		D		C		A		E
8	C		E		D		B		A
9	D		A		E		C		B
10	E		B		A		D		C

A=scopolamine matching placebo SC + TAK-071 matching placebo PO + donepezil matching placebo PO.

B=scopolamine 0.5 mg SC + TAK-071 matching placebo PO + donepezil matching placebo PO.

C=scopolamine 0.5 mg SC + TAK-071 PO + donepezil matching placebo PO.

D=scopolamine 0.5 mg SC + TAK-071 PO + donepezil 10 mg PO.

E=scopolamine 0.5 mg SC + TAK-071 matching placebo PO + donepezil 10 mg PO.

A 3-week (21-day) washout between treatment periods is required because of the long $t_{1/2z}$ of donepezil to minimize the potential for carryover effects.

The planned timing of assessments and meals relative to scopolamine dosing is shown in Figure 4.d.

[figure not shown]
Scopolamine is administered as a single 0.5 mg SC injection.

TAK-071 or matching placebo is administered as a single PO dose (as DIC) 24 hours before scopolamine administration.

The dose of TAK-071 for Part 2 is selected depending on the results from Part 1 (initial substudy) and the FIH Study TAK-071-1001; however, under no circumstances does the selected TAK-071

dose exceed the maximum tolerated dose (MTD), or if the MTD is not attained, the highest dose tested in the SRD part of the FIH study.

Figure 4.d PK/Pharmacodynamic (PD) Assessments and Meal Timing Relative to Scopolamine Administration – Part 2

Note: Solid gray PK/PD symbols indicate predose assessments. Numbers inside symbols indicate scheduled times relative to the respective study drug dosing for the PK analyte. Shaded meal symbols indicate low-calorie, low-fat meals; all other meals are standard.

[figure not shown]
The precise dosing time of TAK-071 relative to scopolamine is selected to ensure that both drugs reach their anticipated peak effects at approximately the same time to maximize the potential to observe TAK-071 procognitive effects.

The precise dosing time of TAK-071 relative to scopolamine is selected to ensure that both drugs reach their anticipated peak effects at approximately the same time to maximize the potential to observe TAK-071 procognitive effects.

Donepezil (10 mg) tablet (overencapsulated) or matching placebo is administered as a single capsule PO 3 hours before injecting scopolamine to maximize the chances of observing a reversal of the scopolamine-induced cognitive impairment.

Blood samples for the analysis of TAK-071, scopolamine, and donepezil plasma concentrations are obtained at specified time-points up to 10 hours after scopolamine dosing.

CCI

Information on the safety and tolerability of TAK-071 in combination with scopolamine and/or donepezil is obtained from treatment periods in which active TAK-071 is administered (Treatments C and D). Safety and tolerability are obtained during Treatment A for placebo, Treatment B for scopolamine alone, and during Treatment E for donepezil in combination with scopolamine.

4.0 ANALYSIS ENDPOINTS

Note: Some of the planned endpoints have been removed or modified due to the early study termination. See Section 7.10.17.13 for details.

5.1 PRIMARY ENDPOINT

No longer applicable.

5.2 SECONDARY ENDPOINTS

- Percentage of subjects who have at least 1 treatment-emergent adverse event (TEAE).
- Percentage of subjects who meet the Takeda markedly abnormal value (MAV) criteria at least once postdose for the following:
 - Clinical laboratory parameters.
 - Vital sign measurements.
 - ECG parameters.
- PK parameters of TAK-071 in plasma after a single dose on Day 1, for Part 1 only, as follows:
 - Maximum observed plasma concentration (C_{\max}).
 - Time of first occurrence of C_{\max} (t_{\max}).
 - Area under the plasma concentration-time curve from time 0 to time of last quantifiable concentration (AUC_{last}).
 - Area under the plasma concentration-time curve from time 0 to time t (AUC_t).
 - Area under the plasma concentration-time curve from time 0 to infinity (AUC_{∞}), as permitted by the data.
 - $t_{1/2z}$ in plasma, as permitted by the data.

5.3 EXPLORATORY/ADDITIONAL ENDPOINTS

No longer applicable

5.0 DETERMINATION OF SAMPLE SIZE

For Part 1, a sample size of 6 enrolled and 4 completers is considered sufficient for providing guidance on the TAK-071 dose selection for Part 2, the main study. This is not based on any statistical power.

For Part 2, a sample size of 26 subjects, approximately 3 subjects for each of the 10 sequences of the 5-period cross-over, is used and is considered sufficient for evaluation of the primary cognitive endpoints for this study based on consideration of published scopolamine model literature and expert advice. Subjects who drop-out are not replaced, therefore to ensure there are enough completers a total of 40 subjects are recruited (4 per sequence).

In particular, this sample-size calculation was based on a consideration of effect sizes seen in a similar study [5]. Using a 2-sided alpha level of 0.05, this study has a 90% power to detect an effect size of 0.67 in the GMLT (sum of 5 trials) total number of errors for the primary treatment comparison of TAK-071 + scopolamine vs placebo + scopolamine, assuming a total of 26 subjects complete the study and provide primary endpoint data.

At least 26 subjects will complete the study if 40 subjects are randomized, assuming the drop-out rate does not exceed 33%.

6.0 METHODS OF ANALYSIS AND PRESENTATION

7.1 GENERAL PRINCIPLES

This Statistical Analysis Plan (SAP) was developed based on International Conference on Harmonization E3 [6] and E9 [7] Guidelines. This SAP should be read in conjunction with the study protocol and electronic case report forms (eCRFs). This version of the SAP was developed using the information provided in Protocol TAK-071-1002 Amendment 02, dated 10 March 2017 [8].

All study-related raw data, including derived data, will be presented in data listings. Continuous data will be summarized using: number of subjects (N), mean, standard deviation (SD), median, minimum, and maximum, where appropriate. Where indicated, coefficient of variation (CV%) and geometric mean will also be included in the summary of continuous data. Categorical data will be summarized using the number and percentage of subjects for each category where appropriate.

All statistical tests will be 2-tailed at $\alpha=0.05$ level for significance unless otherwise stated. The p-values less than or equal to α (when rounded to three digits) are reported as “significant”. The phrase “no significant difference” indicates that all p-values for the tests are greater than α . All computations will be performed prior to rounding.

Due to the timing of the early study termination, no subjects began Period 2 and only 12 subjects were enrolled in Part 2. Therefore all data for Part 2 will be summarized by treatment, but not by sequence.

7.1.1. MISSING DATA

There will be no imputation of incomplete or missing data. Decisions regarding inclusion or exclusion of data from an analysis for subjects who are noncompliant with the dose schedule, or who have incomplete data, will be made on a case-by-case basis, but the data will be presented in data listings regardless.

Plasma concentrations that are below the limit of quantification will be treated as zero in the summarizing of concentration values and deriving of PK parameters. These values will be flagged in the data listings, and deviations from this convention may be considered on a case-by-case basis as deemed appropriate.

7.1.2. DERIVED DATASETS AND VARIABLES

Derived datasets will be generated according to CDISC guidance documents: Analysis Data Model (ADaM) Implementation Guide, Version 1.0 (17 Dec 2009); ADaM Data Structure for Adverse Event Analysis, Version 1.0 (10 May 2012).

Body mass index (BMI) will be calculated as $\text{weight (kg)}/(\text{height (m)})^2$ and will be presented to 1 decimal place. BMI will be calculated for Screening.

7.1.3. DEFINITION OF STUDY DAYS AND BASELINE

For all safety endpoints, Baseline is defined as the last non-missing measurement prior to first dose of study drug for subjects in Part 1. Baseline is defined as the last non-missing

measurement prior to first dose of study drug in the respective treatment period for subjects in Part 2, unless otherwise specified.

For all safety endpoints in Part 2, study day will be calculated relative to the date of first dose in the respective treatment period. Study day prior to the first dose of treatment in the respective treatment period will be calculated as: date of assessment/event – date of treatment; study day on or after the first dose of treatment in the respective treatment period will be calculated as: date of assessment/event – date of treatment + 1.

7.2 ANALYSIS SETS

Safety Set

The safety analysis set consists of all subjects who are enrolled and received 1 dose of study drug. Subjects in this analysis set are used for demographic, baseline characteristics, and safety summaries.

Pharmacokinetic Set

The PK set consists of all subjects who receive study drug and have at least 1 measurable plasma concentration. All subjects with valid PK parameter estimate will be included in the summaries and analyses for that parameter.

If any subjects are found to be noncompliant in dosing schedule or with incomplete data, a decision will be made on a case-by-case basis as to their inclusion in the PK analysis but will be presented in the subject listings.

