4.3 Benefit/Risk Profile

There is no expected clinical benefit for subjects entering this study. The risks of participation are primarily those associated with adverse reactions to the study drugs. There may also be some discomfort from collection of blood samples and other study procedures.

While extensive clinical safety and efficacy data are available from other cholinomimetic agents, such as donepezil, there are currently no safety data from clinical studies in the public domain for other M_1 R PAMs. The safety data from nonclinical studies with TAK-071 and clinical data from other cholinomimetics, such as donepezil, include side effects such as diarrhea, nausea, and vomiting secondary to the pharmacologic activity of the compound [17]. At the time of start of this study, safety, tolerability, and PK data will be available from all SRD study cohorts from the first-in human (FIH) study. This proof of mechanism study may therefore only start after completion and review of the SRD cohorts and confirmation of the acceptable single-dose safety, tolerability, and PK of TAK-071.

Scopolamine may cause drowsiness, dizziness or blurred vision [18]. Therefore, to minimize the risk to subjects (ie, due to driving or operating dangerous machinery), subjects will be kept at the study center for at least 8 hours and will only be allowed to leave the study center earlier than 8 hours upon confirmation by the investigator or designee that scopolamine effects have worn off.

The most common adverse events (AEs) for donepezil are diarrhea, muscle cramps, fatigue, nausea, vomiting, dry mouth, and insomnia [17]. Donepezil has been previously administered to healthy subjects in the context of multiple phase 1 clinical trials, including bioequivalence trials [19,20] as well as in other scopolamine challenge studies ([21,22] and [Study ROF-ALZ_102]), indicating that single doses of 10 mg are safe and well tolerated in this population.

It is not expected that this study will result in any therapeutic benefit for the included study population. However, data generated from this study should enable the investigation of TAK-071 in subsequent clinical efficacy studies of longer duration in the relevant subject populations (ie, phase 2).

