This is a randomized, double-blind, sponsor unblinded, placebo-controlled, 5-treatment, 5-period, 10-sequence crossover phase 1b proof of mechanism study to evaluate the effects of a single PO administration of TAK-071, a novel M₁R PAM, on scopolamine-induced deficits in cognitive function in healthy adult male subjects.

Approximately 40 subjects are expected to be randomized in this study, with the total of 4 subjects per sequence and with a minimum of 3 completers. A schematic of the study design is provided in [Figure 6.c](#).

Figure 6.c Schematic of Study Design – Part 2

Screening Period	Treatment Periods 1 to 5				Wash-Out Periods 1 to 4	Follow-Up
Screening and Pre-Enrollment Enrichment	Check-in	Baseline PD	Single Dose PK/PD	PK/PD		Follow-up Telephone Call/Visit
Days -56 to -2	Day -1	Day 1	Day 2	Day 3	Days 4 to 20	Day 9 (±2) Period 5
	←—Confinement—→					

6.2.1 Pre-Enrollment Enrichment Screening – Part 2

To ensure that enrolled subjects will show cognitive impairment in the presence of scopolamine but with minimal sedation and/or fatigue, all subjects who meet Screening inclusion/exclusion criteria will be administered an SC dose of scopolamine 0.5 mg.

Pre-enrollment enrichment procedures will be conducted as part of the Screening assessments between 56 and 2 days before Day 1, and the results will be used to accept/reject the subject for enrollment to Part 2, the main study.

Subjects will remain under observation post-scopolamine administration per principal investigator's discretion to ensure that scopolamine-induced effects have worn off and it is safe for the subjects to leave the study center.

Any subject unable to perform the CogState battery after training will be excluded from entering Part 2, the main study.

6.2.2 Treatment Sequences – Part 2

In each period, subjects will check-in at the study site on Day -1 and will be confined until Day 3 (approximately 24 hours postdose of scopolamine or matching placebo).

Subjects will be randomly assigned to 1 of 10 possible treatment sequences (described in [Section 8.1.3](#)) before the first dose of study drug, each consisting of 5 treatment periods ([Table 6.a](#)).

Table 6.a Summary of Treatment Sequences in Study - Part 2

Sequence	Period 1		Period 2		Period 3		Period 4		Period 5
1	A	Minimum 3-week washout	B	Minimum 3-week washout	D	Minimum 3-week washout	E	Minimum 3-week washout	C
2	B		C		E		A		D
3	C		D		A		B		E
4	D		E		B		C		A
5	E		A		C		D		B

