7.3 Additional Inclusion Criteria for Part 2 After Pre-Enrollment Enrichment Screening

1. Subject able to perform the CogState battery.
2. Change from Baseline (average) in total GMLT errors of ≤ -5 at 2 hours postdose of scopolamine.
3. Subjects with sleepiness score <8 on the KSS at 2 hours postdose of scopolamine.
4. Subject passes a hearing test with at least 80% correct responses and no more than 20% false positives. This test can be repeated once to determine eligibility.

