13.1.1 Analysis Sets

13.1.1.1 Safety Set

The Safety Analysis Set will consist of all subjects who are enrolled and received 1 dose of study drug. Subjects in this analysis set will be used for demographics, Baseline characteristics, and safety summaries.

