7.5 DEMOGRAPHIC AND BASELINE CHARACTERISTICS

Demographic and baseline characteristics will be summarized for all randomized subjects by treatment sequence (Part 2 only) and overall total. Summary statistics (N, mean, SD, median, minimum, and maximum) will be generated for continuous variables (i.e., age, height, weight, and BMI, and years of full-time education), and the number and percentage of subjects within

each category will be presented for categorical variables (i.e. gender, race, ethnicity, caffeine consumption, alcohol use, academic qualifications, and smoking status).

Demographic variables of screen failure subjects and reasons for screen failures will be summarized for all subjects who are screened but not enrolled in the study. Individual demographic characteristics, date of informed consent, any available safety data and reason for screen failure will also be presented in the data listing.

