7.11.1 ADVERSE EVENTS

A TEAE is defined as an adverse event or a serious adverse event (SAE) that occurs or gets worse after receiving the first dose of study drug (the dose administered on Day 1 for Part 1 and on Day 1 of Period 1 for Part 2; run-in scopolamine is considered study drug) until the Follow-up Visit/Call or Early Termination. A TEAE may also be a pretreatment adverse event or a concurrent medical condition diagnosed prior to the date of first dose of study drug that increases in severity after the start of dosing.

Adverse event verbatim reported terms will be coded by system organ class, high-level term and preferred term using MedDRA.

TEAE summary tables will include numbers and percentages of subjects experiencing at least one AE by system organ class (SOC) and preferred term (PT) and will be tabulated by treatment group within Part 1 and Part 2. TEAEs will be summarized according to the treatment most recently received prior to the onset of the event.

The following is a list of AE summary tables to be generated:

- Overview of TEAEs.
- TEAEs by SOC and PT at subject and event level.
- Subject Mappings for TEAEs.
- TEAEs by PT.
- Most Frequent TEAEs by PT.
- Most Frequent Non-Serious TEAEs by PT.
- Relationship of TEAEs to Study Drug by SOC and PT.
- Drug-Related TEAEs by SOC and PT.
- Intensity of TEAEs by SOC and PT.
- Intensity of Drug-Related TEAEs by SOC and PT.
- Pretreatment Events by SOC and PT.

If a subject has more than one AE that codes to the same PT, the subject will be counted only once for that PT. If a subject has more than one AE within an SOC category, the subject will be counted only once for that SOC. TEAEs possibly or probably related to study medication will be tabulated in the same manner. TEAEs will also be summarized by maximum intensity.

Most frequent TEAEs are defined as the AEs occurring in at least 2 subjects in any treatment (ie, Treatment A).

Data listings will be provided for all AEs (including pretreatment events for enrolled subjects), AEs leading to study drug discontinuation, SAEs, and AEs resulting in death.

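### The Safety Set requires enrollment, so Part 2 men given run-in scopolamine and then rejected fall outside every TEAE summary, although the SAP calls that dose study drug

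*SAP*

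**What the plan says.** **Safety Set.** SAP 7.2: "The safety analysis set consists of all subjects who are enrolled and received 1 dose of study drug". Its use follows: "Subjects in this analysis set are used for demographic, baseline characteristics, and safety summaries". Protocol 13.1.1.1 agrees: "The Safety Analysis Set will consist of all subjects who are enrolled and received 1 dose of study drug". Protocol 13.1.5 names this set for AE summaries. I found no separate definition of *enrolled* in either document.

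**Enrichment dose.** Under Protocol 6.2.1 and SAP 4.4.3.1, men who meet the Part 2 Screening criteria are given scopolamine 0.5 mg SC, and "the results will be used to accept/reject the subject for enrollment to Part 2, the main study". Protocol 7.3 lists four criteria: ability to do the CogState battery, a GMLT change at 2 hours, a hearing test, and this one: "Subjects with sleepiness score <8 on the KSS at 2 hours postdose of scopolamine".

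**Status of that dose.** SAP 7.11.1 says "run-in scopolamine is considered study drug". Protocol 8.1.1 also counts scopolamine among the study drugs.

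**Men who are rejected.** SAP 7.5 says that "any available safety data and reason for screen failure will also be presented in the data listing". SAP 7.3 and 7.5 summarize the reasons for screen failure, and Protocol 9.1.19 includes PTE/AE among the reason categories. SAP 7.11.1 promises a listing of all AEs and adds that pretreatment events are included for enrolled subjects.

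**The concern.** A safety population is normally everyone who was exposed. Here it has two conditions, and the order of events in Part 2 separates them: the dose comes first, and enrollment depends partly on the reaction to it. Protocol 4.3 warns that "Scopolamine may cause drowsiness, dizziness or blurred vision", and a high sleepiness score after the dose is one ground for rejection. A subject can therefore leave the safety population because of how he responded to a study drug.

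The percentage of subjects with at least one TEAE is a retained secondary endpoint (SAP 5.2). After early termination, safety and PK are all that will be analyzed (SAP 3.0).

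Little other scopolamine-alone data will exist. No subject began Period 2 (SAP 7.1), and each treatment opens 2 of the 10 sequences (SAP Table 4.a). If all 12 men were dosed and allocation was balanced, 12 × 2/10 = 2.4, so about 2 or 3 men received Treatment B. In Part 1, scopolamine always followed TAK-071. The enrichment visit is thus the study's largest exposure to scopolamine alone. No column A to E represents it, and a listing supplies neither a denominator nor an incidence.

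**Working it through.** The plan states no figure on this point, so there is none to reproduce. The check is mainly a reading of the rules in order.

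| Step | Rule | Source | Man dosed and rejected |
|---|---|---|---|
| 1 | Scopolamine 0.5 mg before enrollment | Protocol 6.2.1; SAP 4.4.3.1 | Dosed |
| 2 | Run-in scopolamine is study drug | SAP 7.11.1 | Has had 1 dose of study drug |
| 3 | Enrichment result decides enrollment | Protocol 6.2.1, 7.3 | Not enrolled |
| 4 | Safety Set needs enrollment and a dose | SAP 7.2; Protocol 13.1.1.1 | Outside the set |
| 5 | AE summaries use the Safety Set | SAP 7.2; Protocol 13.1.5 | In no TEAE table |
| 6 | Screen-failure listing and reasons | SAP 7.3, 7.5 | Present here |

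**How many men.** Let N be the number enrolled and f the share of men dosed at enrichment who are not enrolled. Dosed men outside the set = N × f/(1 − f). N is 12 (SAP 3.0) or the planned 40. The documents do not give f, so the values below are assumptions.

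| f | N = 12 | N = 40 |
|---|---|---|
| 0.10 | 1.3 | 4.4 |
| 0.20 | 3.0 | 10 |
| 0.33 | 5.9 | 19.7 |
| 0.50 | 12 | 40 |

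**Direction of bias.** Let a and r be the event rates in accepted and rejected men. The rate in all dosed men is (1 − f)a + f·r, which differs from a by f(r − a). Take f = 0.33 and purely illustrative rates:

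- a = 20%, r = 60%: 0.67 × 20 + 0.33 × 60 = 33.2%, so a summary of accepted men alone is 13.2 points too low.
- The same rates exchanged: 0.67 × 60 + 0.33 × 20 = 46.8%, so it is 13.2 points too high.

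The sign depends wholly on r − a, which the documents do not supply.

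**Which events were collected.** Three rules do not agree for Part 2:

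- Protocol 10.2.1.1 ends PTE collection at the enrichment visit or at screen failure, but starts AE collection at first study drug, which it identifies as Day 1 of Period 1.
- Protocol Appendix A, Part 2 footnote (w), runs PTE collection up to dosing on Day 1.
- SAP 7.11.1 identifies the first dose as Day 1 of Period 1 and in the same sentence counts run-in scopolamine as study drug.

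An event between the enrichment dose and Day 1 could be a PTE, an AE or neither, depending on the rule followed. Appendix A does mark an AE assessment at Screening. Reconciling these rules would not by itself bring rejected men into the Safety Set.

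**The case against.** Several points on the other side are sound and limit the finding.

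- **Rejected men are not invisible.** Their available safety data are listed, their reasons for failure are summarized, and PTE/AE is one of the categories. SAP 7.8 lists dose dates and times for all subjects. In SAP 7.11.1 the words about enrolled subjects qualify pretreatment events only, so the listing of all AEs may reach rejected men, though it does not say so. The gap is in summaries.
- **No treatment comparison changes.** Rejected men never receive TAK-071 or donepezil, and Treatments A to E are all given to men who passed enrichment. The safety objective concerns TAK-071 given with scopolamine.
- **Rejection is not simply intolerance.** Failing the GMLT, CogState or hearing criterion also rejects. The GMLT criterion is meant to keep men who decline under scopolamine (Protocol 6.3.2), so it may remove men less affected by it. The documents also do not make a KSS of 8 or more an AE.
- **The data may be thin.** Enrollment has ended, and a new set definition cannot recover events that were never collected.

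A reader might infer that scopolamine harm is reported only in men selected for tolerating it. The documents do not support that: about 6 Part 1 men receive scopolamine with no enrichment step and are in the Part 1 safety tables, although always after TAK-071. A reader might also infer that MAV rates lose these men. They do not, because enrichment follows all other Screening assessments (Appendix A, Part 2 footnote (k)) and no laboratory, vital-sign or ECG assessment is scheduled for rejected men after that dose.

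What remains is that a listing does not replace a summary for men given study drug, and the rule that drops them depends partly on their response to it.

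**Conclusion.** The point holds for Part 2 TEAE summaries. It rests on the literal text: enrollment follows the enrichment result, and the SAP treats run-in scopolamine as study drug. Any summary of events after that dose, however those events are classified, covers only men who passed.

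The size is unknown. About 1 to 12 men would be left out with 12 enrolled, and about 4 to 40 at the planned size, if 10% to 50% of dosed men were rejected. It is tempting to conclude that the scopolamine AE rate is biased downward. The KSS criterion on its own selects against sedation, but with the other grounds for rejection the net direction is not established. This is a defect in descriptive safety reporting that should be corrected. It does not affect any conclusion about TAK-071.

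**What to change.** 1. In SAP 7.2 and Protocol 13.1.1.1, define the Safety Set as all subjects who received at least 1 dose of any study drug, including enrichment scopolamine, whether or not later enrolled.
2. Add one column for collected events after run-in scopolamine. Use all men dosed at enrichment as the denominator, split into accepted and rejected.
3. Keep columns A to E restricted to enrolled subjects who received that treatment.
4. State in SAP 7.11.1 that the AE and SAE listings cover all dosed subjects.
5. Reconcile Protocol 10.2.1.1, Appendix A Part 2 footnote (w) and SAP 7.11.1 on when PTE collection ends and when AE and TEAE status begins.

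The cost is wording, the reconciliation in step 5 and one extra descriptive column. That column can hold only events actually collected after the enrichment dose, so its footnote should say what was collected in rejected men and for how long.
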